Appendix A: DSMB Chapter for VCU-ART3

Appendix B: Monitoring Plan

Appendix C: Case Report Form and Data Collection Forms

1) PERSONNEL

Name		Role		Institution/ Division			
[name]/PhD			nvestigator	VCU, Cardiology	VCU, Cardiology		
		Co-Principal Investigator		VCU, School of Pharmacy			
[name]		Investigator	\	/irginia Cardiovascular Specialist	s		
[name] [name]		Investigator		VCU, Cardiology			
[name]	Investigator	ator Washington Hospital Center, Cardiology					
[name]		Investigator	Washington Hospital Center, Cardiology				
[name], MS		Research Assistant		VCU, Cardiology			
[name]		Investigationa	al Pharmacy	VCU, Pharmacy	VCU, Pharmacy		
[name]	Adjudicating C	ommittee	VCU, Cardiology	VCU, Cardiology			
[name]	Adjudicating C	ommittee	VCU, Cardiology	VCU, Cardiology			
[name] Event		Adjudicating Committee		VCU, General Medicine			
[name]		DSMB Chair	Un	iversity of Florida, Cardiology			
[name]		DSMB member		VCU, Heart Failure			
[name]		DMSB member		VCU, Infectious disease	VCU, Infectious disease		
[name]		DSMB memb	er	VCU, Cardiology / McGuire VA	١.		
[name]		DSMB memb	er	VCU, General Medicine			
[name]		DSMB coordi	nator	VCU, Johnson Center			
[name]		Consultant		University of Colorado			
[name]		Consultant		Duke University			
[name]		Consultant		Catholic University, Rome, Italy			
[name]		Consultant		Sapienza University, Rome, Italy	y		
[name]		Consultant		VCU, Cardiology / McGuire VA			
[name]		Consultant		VCU, Cardiology			
[name]		Consultant		VCU, Biostatistics			

Abbreviations: DSMB=Data Safety Monitoring Board

2) PROTOCOL SUMMARY

Title: Interleukin-1 Blockade in ST-segment elevation acute myocardial

infarction (STEMI)

Population: 99 patients with STEMI presenting within 12 hours of onset

Site(s): Virginia Commonwealth University, Richmond, VA

> Virginia Cardiovascular Specialists, Richmond VA Washington Hospital Center, Washington DC

Study Duration: 36 months

Description: Phase II clinical trial of Anakinra (standard and higher dose) for 14

> days to quench the acute inflammatory response during STEMI and to prevent adverse cardiac remodeling and heart failure after

STEMI

Objectives: To determine the effects of IL-1 blockade with Anakinra (standard

> and higher dose) on the area-under-the-curve for C-reactive protein (as preferred inflammatory marker in STEMI, and a surrogate for IL-1 activity), the changes in left ventricular dimensions and function,

and the clinical outcomes up to 1 year.

Study Design: Multi-center, randomized, double-blinded, placebo-controlled

[figure not shown]
clinical trial with allocation to Anakinra 100 mg daily, Anakinra 100

mg twice daily, or placebo for 14 days.

Estimated Time to

Complete Enrollment: 24 months

*! A C496 > 2D: 4 A @ A A CDE51 A 5 6 C:8 ? A

+!A\$24<8 B@E?5A:?7@B>2D: @?A2?5AC:8?:7:42?46 A

;Z lk\Ād pfZ Xi[`XeĀe]XiZkfeĀ"; G @#Ā\ d X`ejĀxĀd XafiĀZXIj \Āf]Ād fi Y`[`kpĀxe[Ādf ikXc`)pkĀeĀk_\ĀOMĀxe[Ā nf ic[n`[\(\alpha\) | j g`klĀZ ii\ ekĀjkiXk^`\jĀjfiĀ XiopĀ\ g\i]Ij `fe & Ād XepĀgXk\ ekjĀ[`\ĀXiopĀ[li `e^Āk_\Ā Zfli j\ & Āve[Āk_fj \Ān_fĀj I imm\ĀXi\Āxkā) bĀjfiĀp `e^Āx\klĀjf dĀx[m\ij\ĀzXi[`XZĀ\d f[\c`e^&ā_\Xikā] X`d i\ & Āxe[Ā] [[\eĀ[\ Xk_Ā

jpdgkfdjĀfjĀ[pjge\XĀXe[Ā]Xk^I\ &Āk_\Ā]i\hI\ekĀ_fjg`kXoĀX[d`jj`fejĀ Xe[Ā_k\Ā \Zfefd`ZĀ Zfej\hI\ eZjĀfjkĀgif[IZ km`kpĀxe[Ā`eZi\Xj`e^ĀzfjkjĀf]Ād\[`ZXoĀZKi\&Ā_XikĀ)Ķīdi\Ādgfj\jĀĀ j`^e`]`ZXekĀKli[\ eĀkeĀ\XokZxi\(Ā

N_\i\ĀjĀXĀĪi^\ekĀe\\ [ĀkfĀ\m\cfgĀx[[`kfeXĀkh\xkd\ekjĀkfĀg\m\ekĀ_XikĀ]XkĀ]XkĀ]XkĀ]AKĀ GÇĀN\ĀZii\ekĀki\M\d\ekĀeĀMNPG CĀeZd[\jĀgifdgkĀ\g\i]Ji`feĀf]Āk_\ĀjZ_\d`ZĀdpfZXi[`IdĀYpĀi\jikfiXkfeĀf]Āk_\ĀZifeAĀMNPG CĀeZd[\jĀgifdgkĀ\g\i]Ji`feĀf]Āk_\ĀjZ_\d`ZĀdpfZXi[`IdĀYpĀi\jikfiXkfeĀf]Āk_\ĀZfifeXipĀXikipĀgXkeZpĀ"(\(ĀXe^`fgcXjkpĀfiĀ]`Yi`efcpj`j#&Āgi\m\ekfeĀf]Āi\fZ Zdj`feĀ"(\(ĀXekġcXkc\kĀXe[ĀXekZfX^IcXekj#&ĀkeļĀe\lif_fidfeXcĀYcfZbX[\Ā"`(\Āi\e`e'Xe^`fk\ej`e'X&fjkife\ĀXe[ĀXi\e\lifaXekZfX^IcXekj#&ĀkeļĀe\lif_fidfeXcĀYcfZbX[\Ā"`(\Āi\e`e'Xe^`fk\ej`e'X&fjkife\ĀXe[ĀXi\e\lifaXekZfX^IcXekj#&ĀkeļĀe\lifak_j\āk\j\ākklāe\Zi\e\lifak_j\āk_j\āk\lifak_j\

[figure not shown]

Figure 1. Mortality and morbidity in acute myocardial infarction. The figure highlights how despite (or due to) a reduction in mortality in patients with acute myocardial infarction, the incidence of heart failure (HF) is rising to unanticipated rates. Data from the Framingham cohort. Modified from Velagaleti et al. Circulation 2008.

i\df[\c`&^&_\Xik^A]X`cli\ĀXe[Ā[\Xk_('Ā@`li\Ā,Ā]_fnjĀ_fnĀ\cm\o;Ā='i\XZk`m\Āġfk\`eĀ.X*eĀ.XZlk\Ā g_Xj\Āi\XZkXek#Āki\Ā`eZi\Xj\[Ā`eĀ;GCĀ—X[Āg\i[`ZkāflkZfd\(Æ\

[figure not shown]

Figure 2. Kinetics and prognostic value of CRP increase during STEMI. Data from 138 patients with STEMI show a peak increase in CRP at 72 hours and a significant prognostic value of CRP elevation after STEMI. Modified from Roubille et al. Eur J Intern Med 2010.

Gf[lc XkfeĀf]Āk_\Āe]XddXkfipĀ\j gfej\Āk_i]fi\Āi\gi\j \ekjĀXĀkXr\kĀfiĀek\im\ekfe(ĀQ_`\āĀ gi\m`fljĀkkkd gkjĀkfĀdf[lcXkĀk_\Āe]XddXkfipĀ\j gfej\Ā_XmĀ]X`d[&Ān\Āgif gfj\ĀXĀsfm\cĀxe[Ā jlYj kXekXæpĀ[]]\i\ekĀXæjf XZ_ĀkĀdff [lcXke^Āk_\Āe]XddXkfipĀ\j gfej\Ā_XmĀ]X`d[&Ān\Āgif gfj\ĀXĀsfm\cĀxe[Ā jlYj kXekXæpĀ[]]\i\ekĀXæjf XZ_ĀkĀdff [lcXke^Āk_\Āe]XddXkfipĀ\j gfej\ĀYpĀ,\c\Zkm\æpĀYfoZb`e^Ā Cekidlb `e'+ĀCFĀ\ķĀCFĀ\kāZbX[\ĀdXpĀe[\\[Āigi\j\ekĀXæĀm\æ&ĀX]\ĀXe[Ā]]\ZkmĀXægif XZ_ĀfiĀ k_\Āgi\m\ek`feĀf]Ā\XikĀkcti\Āfcdfn`e^Ā,G Cæftklek`XæpĀtX[`e^ĀkfĀdgifm\[ĀhlXdpĀŋĀc]\&Ā[lZ\[ĀZ]kj&Āke[Ādgifm\[Ā]immXd

@klic\lb`e'+Ā"@F'+#Ā`jĀk_\Āgifkfkpg`ZXcĀ`e]cXddXkfipĀZpkfb`e\Ā`emfcmkā`eĀm`ikXccpām\ipĀ
`e]cXddXkfipĀ\jgfej\Ā`eĀk_\Āyf[p('ĀGfjkpā\c\Xj\[Ā'ypĀxZkm)Xkl[ĀdXZifg_X^\j&ÆF'+ĀXZkjĀteĀxĀ
mXi`\kpĀt]ĀZ\cc;Āk_ifl ^_ĀXZkm)XkfeĀt]Āk_\Ākpg\ĀGā\Z\gkfiĀ'@F'+L+#(ĀFfZXcopĀ'\e\iXkl[ĀGF'+Ā]lik_\iĀ
XZkm)XkkjĀtbfZpkjĀxe[Ā\e[fk_c`XoĀz\c&Āgkkckkkk]XeĀj`YifYckjkj&ĀXjeĀgifdfk\jĀk_\Āi\Zil`kd\ekā
XZkm)XkfeĀs[Āi\k\ek`feĀf]ĀdbfZpkjĀnk `eĀk\ĀjZ\d``ZĀdpfZXi[`ld (ĀĀ

(Ε'+Ā, ``eXc`eĀ, ĀZ`kZXcĂeĀ, G(C'ĀœĀog\i`d\ekXcĀ, GCcĀf Ij\Ād f [\c j &cĀ 'Z\Ān`k_Ā\ e\kZĀ, \d kfeĀf]Ā CF+L+ #ēfkĀ\j gf ej mhĀkfĀŒ'+#Āsi\Āgif k\Zkl [Ājf dĀs[m ij\ĀZxi[`XZĀ\ df [\c`e\&ān_\ i\ XjĀd `Z\Ān`k_Ā '\ e\k'ZĀ, \c\k'f eĀ]Āk\ĀŒ\ +#Āsi\Āgif k\Zkl [Ājf dĀs[m ij\ĀZxi[`XZĀ\ df [\c`e\&ān_\ i\ XjĀd `Z\Ān`k_Ā '\ e\k'ZĀ, \c\k'f eĀ]Āk\ĀEXKi XĀĒ ZZ ii`e^Ā\Z\g kfiĀxekXf e`jkĀ\CF+ Ā\Z\g kfiĀxekXf e`jkĀUCFL XĀ n_`Z_ĀXm Āe_XeZ\[Āi\ jgf ej\ĀfĀŒ'+&Āxm Ān fij\Āxxi[`XZĀ\df [\ce^Āxe[Ā]X'ci\ĀeĀzf dgXi]jf eĀ kfĀk\Ān`c['kpg\Ād`Z\Ān`k_Āzf ii\ jg f e[`e^Ā\ e\ k'ZĀXXZb^if l e[(ĀŒ'+Āvct ZbX[\Ālj `e^Ā\ Zf dY`eXelĀ CF+Ā\Z\ gkf iĀxekXfe`j k&ĀeXb`eiX&Ād\c`f iXk\[Āk\Ān`df [\ce^ĀgifZ\jjāxe[Āi\ [l Z\ād f ikXckp()^0 = f dgXi\[Ā kfĀZf ekifcĀd`ZĀ "ki\ Xkl[Ān`k_ĀgoXZ\ Yf yĀĀj Xċe\Āj fcl kf e#&Āl`Z\Āk\ Xkl[Ān`k_Āg\ idX e\ ekā Zkf ejĀf]ĀxeXb`eiXĀ-Ād\^)b^Ā_X[Ād gifm\ [Ā] li mmXcĀX]k iĀxi^\Āķek i`f iĀ, GcĀl\Āk\Āg\ idX e\ ekā Zf if eXipĀskl i pĀl i^`ZXĀĀ Zdj `f eĀ3. ĀŋĀ. &ā 6* (*/# &Āe[Āx] li mmfi jĀ_X[Ām`[\eZ\Āf]Āl fi\Ā] Xhfi Āg\ idX e\ ekā Zf if eXipĀskl i pĀl i ``ZXĀĀ Zdj `f eĀ3. ĀŋĀ. &ā 6* (*/# &Āe[Āk_Ā] li mmfi jĀ_X[Ām`[\eZ\Āf]Āl fi\Ā] Xhfi Āg\ idX e\ ekā Zf if eXipĀxi [`XZĀ\ df [\ce^Āj] d xcbi ĀĒPĀ e[' [` XjkfcZĀxe[Ā\ e['jpjk f c`ZĀXd\ k\ijĀxe[Ā_ā]]\ ZkjĀf]ĀŒ'+Ā \a\Z kfeĀ] iXkfēĀ] \Ā \a\Z ĀjāĀxĀZ `d\ i`ZĀgifk\ eĀk XkĀve[Ārē-Āvēz b\ ijĀnkĀ] `]\i \ekĀdZ Ze] d jĀĪĀxĀz fe-ĀkjĀvē[` eĀk XkĀve[Ārē-Ārē] Axkē^ĀŒ'+ZĀsēfĀŒ'+ZĀsēfĀŒ'+Ārāji\m\ekĀdZ `d\ i`ZĀgifk\`eĀk XkĀve[ārī Zājā Xkè^ĀĒ'+ZĀsēfĀŒ'+ZĀsēfĀŒ'+Ārāji\m\ekĀdZ `d\ i`ZĀgifk\`eĀk XkĀvē[Ārē] Ārē-Ārā

the membrane receptor, and 2 anti-IL-1β antibody. All IL-1 blockers had similar effects limiting cardiac dilatation and dysfunction without impairing infarct healing.

Anakinra, recombinant human IL-1 receptor antagonist (Kineret™, Biovitrum, Sweden) is approved in USA and Europe for the treatment of rheumatoid arthritis ⁷, and is also highly effective in the treatment of several inflammatory disease, and preliminary studies show benefits also in ischemic and hemorrhagic stroke and diabetes. The favorable safety profile of anakinra is witnessed by the hundreds of thousands of patients who have been treated in the past decades. Anakinra is associated with injection site reactions that are generally mild but occasionally severe. Also, anakinra is associated with an increased risk of infections (mainly upper respiratory infections) but it is not associated with an increased infection-related mortality showing that the infections occurring while on anakinra treatment are generally mild. Moreover, anakinra has been also tested in patients with severe sepsis and shock, and while it did not significantly reduce sepsis-related mortality, in a meta-analysis of all studies showed a favorable trend toward reduced mortality (-18%, P=0.08).

Based on the preliminary data in the animal AMI model and the established safety profile of anakinra, we have conducted 2 separate randomized double blinded pilot studies of anakinra vs placebo in patients with STEMI: the first was a pilot study in 10 patients, Virginia Commonwealth University Anakinra Remodeling Trial VCU-ART pilot study [clinicaltrials.gov NCT00789724].8 completed in 2010, followed by a second study in 30 patients, VCU-ART2 pilot study [clinicaltrials.gov NCT01175018].9 Both studies included patients with reperfused STEMI who were hemodynamically and clinically stable. The 40 patients were followed for 3 months and paired cardiac magnetic resonance analyses. Anakinra was used at a standard dose of 100 mg daily for 14 days. The primary purpose of these pilot studies was to establish safety and feasibility. Mortality and event rates were low in both groups likely reflecting a selection bias toward lower risk STEMI due to the fact that patients had to be stable enough to undergo cardiac MRI at 24 hours: median TIMI STEMI score was indeed 3 (interquartile range 1-4) and only 1 patient died (2.5%) within 3 months of STEMI. Overall anakinra showed an acceptable safety profile with only 2 patients (10%) experiencing adverse event requiring discontinuation of therapy (vs 2 [10%] in placebo, P=0.94). Injection site reactions were the most commonly encountered side effect occurring in 5 (25%) patients in the anakinra group and 2 (10%) in the placebo group. Nine adverse cardiac events (1 death, 2 recurrent MI, 6 new onset heart failure) occurred in 6 placebo patients, whereas 3 adverse cardiac events (2 recurrent MI and 1 new onset heart failure) occurred in 3 anakinra treated patients (P=0.25). Anakinra-treated patients were significantly less likely to experience new onset heart failure (1 patients, 5%) vs placebo-treated patients (6 patient, 30%, P=0.035, Figure 3).

[figure not shown]

Figure 3. Heart failure-free survival after STEMI.

Data from the VCU-ART and VCU-ART2 pilot studies (N=40) suggest a protective effect of anakinra on the incidence of HF after STEMI.

IL-1 blockers are also substantially different from TNF-α blockers, which have shown disappointing results in the treatment of chronic heart failure. Indeed, although the 2 classes are occasionally considered interchangeable for the treatment of rheumatic diseases, they should not. It is true that elevated IL-1β and TNF-α levels often coexist in acute and chronic illnesses and it is also true that TNF- α induces IL-1 β synthesis and release, yet the two cytokines have different dedicated signaling receptors and different signaling pathways. While IL-1 has a single signaling receptor (IL-1R1), TNF-α has 2 membrane receptors (type I and II) with different and opposing actions in the heart. The signaling downstream of the receptors is also different for TNF-α and IL-1 and the pathways are mostly not convergent. This explains the differences in efficacy, safety and tolerability of TNF-α and IL-1 blockers in different diseases. In example, patients with adult rheumatoid arthritis respond more favorably to TNF-α blockers whereas patients with juvenile forms respond more favorably to anakinra. The use of TNF- α blockers is associated with increased risk of reactivation of Mycobacterium tubercolosis infection whereas anakinra is not. Moreover, as a proof of the differences between the 2 cytokines, patients with TNF-related periodic fevers do not respond to IL-1 blockers and patients with cryopyrin-associated periodic syndromes (characterized by enhanced IL-1 activity) do not respond to TNF-α blockers. Therefore the fact that TNF-α blockers have failed to show a benefit in chronic heart failure does not predict whether IL-1 blockers will be effective in AMI, an entirely different clinical condition. In our pilot studies in patients with heart failure 10, anakinra significantly reduced IL-6 and CRP levels but had no effects on TNF- α levels showing that IL-1 blockade does not provide a reduction in TNF- α . Furthermore, anakinra is not immunosuppressive, and actually it has been recently shown to prevent stroke-induced immunosuppression.

In summary, we know that IL-1 activity is enhanced in the heart following ischemia and infarction. Experimental animal studies show a central role of IL-1 in infarct healing and promotion of heart failure. Pilot clinical trials in patients with STEMI or heart failure also show a favorable safety profile and a favorable effect on outcomes. These data represent the basis for hypothesizing beneficial effects of IL-1 blockade in patients with STEMI who show signs of enhanced IL-1 activity and are at high risk for in-hospital and long-term mortality.

5) OBJECTIVES

The current research is designed to investigate the safety and efficacy of Anakinra (standard or higher dose) in patients with STEMI in a randomized double-blinded trial. We hypothesize that anakinra will quench the inflammatory response, improve cardiac remodeling, and reduce the incidence of heart failure.

5.1 Primary Endpoint

The primary endpoint of the study is the difference in the area-under-the-curve (AUC) for CRP between admission and day 14 between anakinra 100 mg daily and anakinra 100 mg twice daily compared with placebo.

Patients presenting with STEMI have an enhanced IL-1 response as witnessed by elevation in serum markers such as CRP.⁴ We anticipate that patients with STEMI will have increased CRP levels and its levels will predict adverse cardiovascular outcomes. We therefore hypothesize that anakinra (standard dose) will blunt the CRP increase during STEMI, as seen in the pilot studies, and that anakinra (high dose) will further reduce CRP compared with placebo and with anakinra (standard dose). The rationale for measuring AUC for CRP is that it integrates measurements across multiple time points to more accurately capture the acute inflammatory response and IL-1 activity, and is also an established prognostic marker in STEMI.

5.2 Secondary Exploratory Endpoints

Additional endpoints will include parameters measured at echocardiography, as well as biomarkers, and clinical outcomes.

Echocardiography: structural and functional echocardiographic parameters include left and right ventricular dimensions, mass, systolic and diastolic function. These will provide mechanistic insight as to whether the hypothesized changes in the acute inflammatory response will correlate with changes in cardiac dimensions or function. The echocardiogram will be ordered acutely (within 24 hours) and at 1-year follow up as clinically indicated.

Biomarkers: Blood will be collected at each time-point throughout the study (admission, 72 hours [or discharge whichever comes first], 2 weeks, 3, 6 and 12 months) and analyzed for complete blood cell count, metabolic markers (including lipids and lipoproteins, glycemic control and insulin resistance, liver and renal panel, sterols), inflammatory markers (i.e. high sensitivity CRP) and cardiac biomarkers (i.e. NT-proBNP and troponin I). The data will be collected and electronically stored for further analysis at the conclusion of the study. When feasible, results from clinically indicated studies will be used.

Clinical outcomes: Incidence of death (cardiac and non-cardiac), hospitalizations (for HF, for other cardiac causes not related to HF, or for non-cardiac reasons) will be recorded at each time-point throughout the study (discharge, 2 weeks, 3, 6 and 12 months) in every patient, and then once at the end of study, by review of chart and/or telephone interview. The investigators and clinicians caring for the patients will remain blinded to treatment allocation and to the CRP data. Adjudication of events will be performed by an *ad hoc* committee blinded to treatment allocation and to CRP data.

6) ENROLLMENT IN THE STUDY

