7.7 Biomarkers assessment

Blood samples will be taken from a peripheral vein at admission, 72 hours, 14 days and 3, 6 and 12 months.

One EDTA-containing tube, one SST containing tube, one Serum Separator Clot Activator tube and one PPT tube will be used for analysis of plasma levels of biomarkers by the True Health Diagnostics LLC, Richmond, VA.

One sodium heparin tube will be used to analyze cytokines markers.

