[] ([] I [] N Bod Bloc	JDY ITEMS: (check all completed) Consenting; [] Initial Labs (local/ce Investigational drug first dose admi Medication Reconciliation; [] Echo dy weight:kg/lb He od Pressure:/ mmHg H 72 h Labs (±12 hours) (local/central	nistered on cardiogram eight:n R:mir	// ordered (poss n/ft n	at:AM/PM ibly <24 hrs) BMI:kg/m ²		
[] h [] v [] a [] r Dura	spital outcomes (check all that appl hypotension/shock, check [] if requipulmonary edema, check [] if requipulmonary edema, check [] if requipulmonary enal failure, check [] if requipulmonary en	uiring inotro uiring mecha f sustained, iring renal re PCI; [] stage	inical ventilati requiring card eplacement th	on lioversion		
[] [[] F [] C	CHARGE PLANNING: (check all com Dispensing of investigational drug (Patient education on drug handling Outpatient Hospital Follow up (11-1 Discussed with patient how to cont	syringe , storage, an L7 days) sche	d self-adminis eduled on	stration (by) (location))	

	VCU-ART3 Subject # Initials Clinical Site: VCU / VCS / WHC						
	Follow up visit #1: 14 day (11-17 days)						
Date of STEMI, Date of F/U visit							
[] [] []	ical conditions: (check all that apply) recurrent angina/myocardial infarction, check [] if leading to re-hospitalization heart failure symptoms, NYHA class (I→IV), check [] if re-hospitalization re-hospitalization for other cause (complete dedicated sheet) death, check [] if presumed cardiac death, check [] if sudden death res						
[]	t Medical History: (changes vs prior – new diagnoses); []; []; []; []						
[] [] [] Boo	Assessment of compliance with investigational drug performed by used syringes; returned syringes) Send-out Labs (HDL); [] Medication reconciliation; Scheduling F/U visit for, location ly weight:kg/lb						
	Follow up visit # 2: 3 months (10-14 weeks)						
Dat	e of STEMI, Date of F/U visit						
[] [] []	recurrent angina/myocardial infarction, check [] if leading to re-hospitalization heart failure symptoms, NYHA class (I→IV), check [] if re-hospitalization re-hospitalization for other cause (complete dedicated sheet) death, check [] if presumed cardiac death, check [] if sudden death res						
[]	t Medical History: (changes vs prior – new diagnoses); []; []; []; es;						
[] [] Boo	IDY ITEMS: (check all completed) Send-out Labs (HDL); [] Medication reconciliation; Scheduling F/U visit for, location ly weight:kg/lb						

,	VCU-ART3 Subject #	Initials	Clinical Site:	VCU / VCS	S / WHC

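### The plan does not tie the three CRP samples behind the primary AUC to one laboratory, and 7.8 sends results to people whom 5.2 keeps blinded to CRP

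*Combined protocol and SAP*

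**What the plan says.** Section 5.1 defines the primary endpoint as the "difference in the area-under-the-curve (AUC) for CRP between admission and day 14". Under 7.7, "Blood samples will be taken from a peripheral vein at admission, 72 hours, 14 days and 3, 6 and 12 months", so three samples fall inside the AUC window.

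On the laboratory, the text and the forms differ:

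- **5.2, Biomarkers.** The list includes "inflammatory markers (i.e. high sensitivity CRP" and the paragraph closes with "When feasible, results from clinically indicated studies will be used". The same sentence stands under the schedule table in 7.8, which has its own hs-CRP row. Neither place makes an exception for CRP.
- **7.7.** The listed tubes "will be used for analysis of plasma levels of biomarkers by the True Health Diagnostics LLC". Section 7.8 ships samples to the same laboratory.
- **Appendix C, patient cover sheets.** The baseline draw may go to HDL or VCU. The 72-hour and 14-day draws are marked HDL only.
- **Appendix C, Initial Assessment form.** The 72-hour item reads "72 h Labs (±12 hours) (local/central", and the initial labs carry the same choice.
- **Appendix C, Enrollment Check List.** The enrollment sample goes to a VCU laboratory that the form itself calls central.

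On blinding, 5.2 states: "The investigators and clinicians caring for the patients will remain blinded to treatment allocation and to the CRP data". Section 7.8 has the laboratory's results sent to the coordinating investigator at VCU and to each center, with no carve-out for CRP.

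**The concern.** An AUC built from three samples is comparable between patients only if the samples are measured in the same way. Here a baseline or 72-hour value from a hospital laboratory could be joined to a send-out value at day 14. Practice could also differ between the three sites. No section requires one assay or one laboratory per patient, or any cross-calibration, and the analysis in 12.3 names no laboratory or site term that could absorb a difference.

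The blinding issue is separate. Section 9.1 blinds the adjudicators to CRP because treatment may affect it, and 12.2 expects the standard dose to halve the AUC and the high dose to halve it again. A post-dose CRP is therefore informative about allocation. The protocol recognizes this in 5.2 and then routes the results to the people it means to blind.

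**Working it through.** **1. The laboratory for each AUC sample**

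| Sample | 7.7 and 7.8 | Cover sheet | Other forms |
|---|---|---|---|
| Admission | outside laboratory | HDL or VCU | local/central; check list: VCU |
| 72 h | outside laboratory | HDL | local/central |
| Day 14 | outside laboratory | HDL | send-out (HDL) |

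I read HDL as the outside laboratory because the visit forms label it send-out; the forms do not say so outright. Day 14 is consistent. Baseline is open, and at 72 hours the two forms contradict each other.

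**2. Weight of each sample.** The plan gives no AUC rule, so I assume trapezoids on days 0, 3 and 14:

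- day 0: 3/2 = 1.5
- day 3: 3/2 + 11/2 = 7.0
- day 14: 11/2 = 5.5

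These sum to 14, giving shares of 10.7%, 50.0% and 39.3%. Baseline and 72 h together carry 8.5/14 = 61%.

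**3. Shift in one patient's AUC.** Illustrative course 5, 50 and 10 mg/l; assumed assay difference 10% to 20%. Neither comes from the documents.

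AUC = 1.5×5 + 7×50 + 5.5×10 = 7.5 + 350 + 55 = 412.5.

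- Only baseline local: 0.10×7.5/412.5 = 0.2%; 0.20×7.5/412.5 = 0.4%.
- Baseline and 72 h local: 0.10×357.5/412.5 = 8.7%; 0.20×357.5/412.5 = 17.3%.

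The size therefore depends almost entirely on which 72-hour form entry governs.

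**4. Effect on power.** Inputs from 12.2: 33 per group, AUC 175±150 (standard dose) and 88±75 (high dose), alpha 0.025.

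The plan's figure first: SE = √((150² + 75²)/33) = 29.19, and 87/29.19 = 2.98.

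- One-sided 0.025: Φ(2.98 − 1.96) = 84.6%, matching the stated 85%.
- Two-sided 0.025, the level given in 12.3: Φ(2.98 − 2.24) = 77.0%.

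The mismatch in sidedness is a separate matter, so both are carried forward.

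Now let the choice of laboratory add an independent, unbiased multiplicative error with CV c to every patient's AUC. Each variance becomes SD²(1 + c²) + mean²·c². For c = 0.20:

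- standard dose: 22,500×1.04 + 30,625×0.04 = 24,625
- high dose: 5,625×1.04 + 7,744×0.04 = 6,160
- SE = √(30,785/33) = 30.54, and 87/30.54 = 2.85

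| c | One-sided 0.025 | Two-sided 0.025 |
|---|---|---|
| 0 | 84.6% | 77.0% |
| 10% | 83.8% | 75.9% |
| 20% | 81.3% | 72.8% |

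The loss is about 1 to 4 points, and that supposes every patient is affected.

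**5. Blinding.** No calculation applies. Section 5.2 blinds investigators and treating clinicians to CRP; 7.8 delivers results to the coordinating investigator and each center. The two cannot both be followed for post-dose CRP. The baseline value is different: the check list places the blood draw before the first dose, so it cannot reveal allocation.

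**The case against.** The sentence on clinical results looks like a general economy measure. It closes a paragraph that also covers blood counts, lipids, liver and renal panels and troponin, and it recurs for echocardiography in 7.6. The local/central entry covers all 72-hour labs, and that visit includes a blood count, so both kinds of laboratory may be meant without CRP being measured locally. Section 7.7 also provides for a centrally analyzed sample at every time point. No section says that CRP is ordered clinically or that the assays differ. All of this stands. It shows that mixing is permitted, not that it is planned or frequent. It does not remove the permission, because the one analyte that needs an exception has none.

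Three stronger readings are tempting and not supported:

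- **The 9% to 17% shift as the effect on the trial.** That range is for one invented course with 72 h measured locally. The cover sheet points the other way, and if it governs the shift is under 1%.
- **Bias between arms.** Allocation is randomized and blinded, so the source of a CRP value should not differ systematically by group. Between-patient SDs are already 71% to 86% of the mean (250/350, 150/175, 75/88), so moderate assay noise adds little.
- **CRP in the medical chart as a stated breach of blinding.** No section says that CRP is filed there. A clinically ordered post-dose CRP would be visible to the treating team, but that is an inference. The conflict in the text is the reporting sentence in 7.8, and moving all CRP to the outside laboratory would not by itself resolve it.

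**Conclusion.** The point holds in two parts. First, the plan leaves open which laboratory measures the baseline and 72-hour CRP, so one patient's AUC may mix laboratories. The frequency and the size of any assay difference are not stated. On the assumptions above, the cost is mainly noise worth about 1 to 4 points of power for high versus standard dose, and an individual AUC could move by anything from under 1% to about 17%. Second, 7.8 contradicts 5.2 on who may see CRP. This part rests on the text alone and needs no assumption. The primary endpoint is a laboratory value and the adjudicators are separately blinded to CRP, which limits the consequence without removing the contradiction. Overall this is a cheap improvement to wording and forms, not a flaw that threatens the trial.

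**What to change.** - In 5.2 and 7.8, exempt hs-CRP from the use of clinical results. State that the admission, 72-hour and day-14 samples are all measured in the laboratory named in 7.7, with one assay.
- Align Appendix C: the same laboratory for all three draws on the cover sheets, the Initial Assessment form and the Enrollment Check List, with CRP separated from labs that may be run locally.
- Use a local CRP value only if the central sample is lost. Flag it, and drop it in a sensitivity analysis.
- In 7.8, withhold post-dose CRP results from the coordinating investigator and the centers until unblinding, so that it agrees with 5.2. Other laboratory results can be reported as now.
- Leave clinically indicated CRP testing unrestricted. The change concerns which values enter the endpoint and who receives the study results.

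The cost is mostly wording. Because the baseline draw may now go to VCU, a few more baseline shipments may be needed, and the sensitivity analysis will have slightly fewer values.
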